5.5 Use of Center for Magnetic Resonance Research: n/a

6.0 Data and Specimen Banking

6.1 Storage and Access: De-identified data will be stored in Box, for future use by other researchers. Data will be available immediately following the first publication with no end date following article publication. Researchers (including those outside of the study) whose proposed use of the data has been approved by PI will have access to the data for individual participant data meta-analysis/to achieve aims in the approved proposal. The AHC-IE will be not used.

Publishing of these data may be required. Federal funders (e.g. National Institutes of Health), granting agencies (e.g. Bill & Melinda Gates Foundation), and journal publishers (e.g. PLoS) increasingly require datasets be made publicly available—often immediately upon associated article publication. If this is the case, all data published will be fully de-identified.

MEDICAL PROTOCOL (HRP-590)

PROTOCOL TITLE: Mechanisms of a Dynamic Stability Approach

VERSION DATE: 05/25/2023

6.2 Data: The following deidentified data may be banked for future analyses and compilation into larger datasets: clinical and demographic information, clinical assessments, and imaging data.

6.3 Release/sharing: Should the investigators pursue data sharing, future studies seeking to compile data acquired from this protocol will obtain IRB approval before doing so. In the event that this occurs, only investigators or study personnel listed in an IRB-approved protocol pertaining to the data compilation will have access to this data. The requested will be released to the researchers in a de-identified manner.

6.4 Sharing of genetic testing: N/A

7.0 **Sharing of Results with Participants.**

7.1 Sharing of results with participants: We plan to share a brief summary of aggregated study results with participants either by email or USPS delivery depending on the participant's preference and will include a "thank you" note for participating. We plan to use the CTSI Dissemination Toolkit when framing the language.

8.0 **Study Population**

8.1 Inclusion Criteria: will include:

- Adults 18 years or older
- having radiographically-confirmed thumb CMC OA
- having been referred to occupational therapy.

A study orthopedist will use current radiographic evidence to screen and stage thumb CMC OA in all prospective candidates to ensure the diagnostic criteria required for inclusion are met. The same study orthopedist will screen recruits for pregnancy or risk of pregnancy via an interview. Both men and women will be included given the findings of Wilder et al.²⁹, who described the prevalence of radiographically confirmed thumb carpometacarpal osteoarthritis to be similar in men (20%) and women (21%).

In addition, should these recruitment efforts prove to be slow we will recruit through the existing health records of adults ages 18 and older who have a diagnosis of CMC OA and have received care within University of Minnesota Health/Fairview orthopedics/ Sports Medicine, or Rheumatology departments from December 2015 to April 30, 2023 Eligible participants will have any of the following ICD 10 codes: Primary OA CMC joint (M18.11, M18.12, M18.2), post-traumatic OA CMC joint (M18.31, M18.32, M18.4) and other secondary OA CMC joint (M18.51, M18.52) and will be identified via the I2B2 Data set and then run by BPIC and sent to Fairview for mailing. Alternatively, Fairview's Research Recruitment services may perform the same service.

Those recruited in this fashion will be required to be screened for pregnancy or risk of pregnancy via an interview by their preferred medical provider (i.e., women's health, family physician, internal medicine, orthopedic surgeon) prior to enrollment.

8.2 Exclusion Criteria will include:

- cortisone treatments to the affected thumb within the prior three months
- thumb CMC joint replacement
- a diagnosis of inflammatory arthritis
- a diagnosis of Ehlers Danlos Syndrome
- a diagnosis of Marfan's disease
- pregnancy or questionable pregnancy
- mothers who are breastfeeding

MEDICAL PROTOCOL (HRP-590)

PROTOCOL TITLE: Mechanisms of a Dynamic Stability Approach

VERSION DATE: 05/25/2023

- cognitive disorders which would preclude a client from following the testing commands and home program participation
- a diagnosis of a concomitant condition affecting the arthritic thumb (i.e. Wartenberg's syndrome, deQuervain's, trigger thumb, intersection syndrome)
- grade 4 Eaton²⁹ OA staging
- ongoing hand rehabilitation (i.e., within prior 6 months)
- pain which precludes participants from completing testing
- an EMR flag for not wishing to participate in research

8.3 Screening: [name] has provided the CTSI's BPIC service with the diagnostic inclusion criteria for the study and will be informed within 3-5 days if a patient who meets these criteria is scheduled at the MHealth Clinics and Surgery Center. [name] will be present during the Study Orthopedist's clinic when these potentially eligible patients are scheduled for appointments. A study orthopedist will use current radiographic evidence to screen and stage thumb CMC OA in all prospective candidates to ensure the diagnostic criteria required for inclusion are met. The same study orthopedist will screen recruits for pregnancy or risk of pregnancy via an interview and present the study to the eligible patient. If the recruit is interested, the informed consent process will follow and will be conducted by [name] or other IRB-approved personnel.

9.0 Vulnerable Populations:

9.1 Vulnerable Populations

Population / Group	Identify whether any of the following populations will be targeted, included (not necessarily targeted) or excluded from participation in the study.
Children	Excluded from Participation
Pregnant women/fetuses/neonates	Excluded from Participation
Prisoners	Excluded from Participation
Adults lacking capacity to consent and/or adults with diminished capacity to consent, including, but not limited to, those with acute medical conditions, psychiatric disorders, neurologic disorders, developmental disorders, and behavioral disorders	Excluded from Participation
Non-English speakers	Excluded from Participation
Those unable to read (illiterate)	Excluded from Participation

MEDICAL PROTOCOL (HRP-590)**PROTOCOL TITLE: Mechanisms of a Dynamic Stability Approach****VERSION DATE: 05/25/2023**

Employees of the researcher	Excluded from Participation
Students of the researcher	Excluded from Participation
Undervalued or disenfranchised social group	Included/Allowed to Participate
Active members of the military (service members), DoD personnel (including civilian employees)	Included/Allowed to Participate
Individual or group that is approached for participation in research during a stressful situation such as emergency room setting, childbirth (labor), etc.	Excluded from Participation
Individual or group that is disadvantaged in the distribution of social goods and services such as income, housing, or healthcare.	Included/Allowed to Participate
Individual or group with a serious health condition for which there are no satisfactory standard treatments.	Excluded from Participation
Individual or group with a fear of negative consequences for not participating in the research (e.g. institutionalization, deportation, disclosure of stigmatizing behavior).	Excluded from Participation
Any other circumstance/dynamic that could increase vulnerability to coercion or exploitation that might influence consent to research or decision to continue in research.	Excluded from Participation

9.2 Additional Safeguards: All participants will be informed that their participation is voluntary, all of the information gathered throughout the course of the study will be kept confidential, and that choosing to not participate at any time in the study will not affect their relationship with the university or their health care providers. Furthermore, participants will be asked, at the time of seeking informed consent, to share their comfort with reading the consent form or any other study materials. If the prospective participant shares that they are uncomfortable with reading the materials, all materials will be read aloud and participants will be asked to do a teach-back to ascertain comprehension.

MEDICAL PROTOCOL (HRP-590)

PROTOCOL TITLE: Mechanisms of a Dynamic Stability Approach

VERSION DATE: 05/25/2023

Undervalued or disadvantaged people may not be known, research staff will not be asking a direct question about socioeconomic status to potential participants. We do not anticipate vulnerability for this group to be increased by participating in this study.

Members of the military may not be known, research staff will not be asking a direct question about military status to potential participants. We do not anticipate vulnerability for this group to be increased by participating in this study.

Undervalued or disadvantaged people may not be known, research staff will not be asking a direct question about socioeconomic status to potential participants. However, we have taken special precaution to make sure participants are fairly and adequately compensated for their time in this study, yet not coerced by unreasonably high compensation amounts.

9.3 Rationale for exclusion (if potential for direct benefit): We plan to exclude expecting mothers/or women who are potentially expecting due to risk of exposure to ionizing radiation. This will impact very few potential recruits given that persons with thumb CMC OA are primarily post-menopausal women. We will exclude persons who are non-English speaking or illiterate because the Michigan Hand Questionnaire is only cross-validated in Brazilian Portuguese, Colombian Spanish and German and requires basic literacy to complete.

10.0 Local Number of Participants

10.1 Local Number of Participants to be consented: we plan to enroll as many as 50 and as few as 40 participants.

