Preliminary retrospective evidence suggests patients who participated in the DS program have better pain and disability outcomes than those who received standard care alone.^{9,10} However, major gaps in evidence for DS remain. Although evidence suggests that surgically stabilizing the thumb CMC improves hand function¹¹, the hypothesized sustained stabilizing effects of the DS exercise program have not been tested in prospective research. It is important to know whether a six week course of a DS program can reduce thumb instability and whether these benefits are possible for patients with a range of CMC OA severity. Additionally, because the gold standard of evaluating thumb instability is not within the scope of practice of rehabilitation scientists and therapists, they are limited in their abilities to visualize thumb CMC joint mechanics when treating and when evaluating response of treatment. Rehabilitation therapists and scientists can, however, be certified in musculoskeletal sonography and sonographic methods can be used to quantify thumb CMC alignment.¹² However, the agreement between sonographic and fluoroscopic or computerized tomography (gold standard) measures for assessing thumb CMC instability is unknown and must first be established.

The *long term goal* of my research is to help *mitigate the pain and disability experienced by persons with upper limb musculoskeletal disorders through non-invasive and non-pharmacological approaches*. The proposed research aims to prospectively evaluate the impact of DS exercises on the thumb instability in persons with thumb CMC osteoarthritis. My training plan supports this long-range goal by providing me the background needed to measure and/or interpret the outcomes of interest and carry out a single-arm intervention study.

We expect, in part, to achieve our long term and training plan objectives by pursuit of these **two specific aims:**

1. To describe changes in radiographic thumb CMC joint misalignment following a 6-week clinic-based dynamic stability exercise program. Fifty patients will be enrolled in a prospective pre-post interventional study of a 8-week clinic-based dynamic stability program and will undergo computerized tomography (CT) measurements before treatment, and upon completion of the program (9 weeks). The primary outcome will be change in CMC subluxation in cm from pre-treatment to post-treatment at 9 weeks.

MEDICAL PROTOCOL (HRP-590)

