Home program	15-20 minutes Daily, 5 days a week	15-20 minutes Daily, 5 days a week	15-20 minutes Daily, 5 days a week	15-20 minutes Daily, 5 days a week	15-20 minutes Daily, 5 days a week	15-20 minutes Daily, 5 days a week	15-20 minutes Daily, 5 days a week	15-20 minutes Daily, 5 days a week
	Approximate duration of treatment per participant							840-1040 minutes

For **aim #2**, ultrasound measures will be obtained using a Sonosite X-Porte sonographic device. Sonographic assessment will occur at the time of participants'

MEDICAL PROTOCOL (HRP-590)

PROTOCOL TITLE: Mechanisms of a Dynamic Stability Approach

VERSION DATE: 05/25/2023

baseline and 9-week CT assessments (aim #1). The PI will conduct sonographic measures of radial subluxation on all Aim #1 participants (n=49). The same stress view, positioning jig and standardized upper limb postures used for Aim #1 will again be employed. In addition to these standardized joint postures and forces, the thumb CMC joint sonographic procedures described by Oo et al.¹² and the general guidelines put forth by American Institute of Ultrasound in Medicine³⁷ will be followed. The device is the property of [name] and there will be no charges billed to the participant associated with the use of this instrument. [name] will work with [name] from Fairview's biomedical engineering dept. to ensure the device is approved for use at the MHealth Clinics and Surgery Center.

The PI will quantify radial subluxation (cm) of the thumb metacarpal in the same manner as it was in Aim #1. The agreement between these values and those gathered through CT in Aim #1 will subsequently be assessed. The PI and the orthopedic surgeon evaluator will be blinded to each other's ultrasonography and CT findings.

The intervention and baseline diagnostic fluoroscopic assessment are standard care and would be conducted even if not for the purposes of this study. Sonography and the CT measurements would be considered above and beyond standard care.

Data to be pulled from patient records include age, sex at birth, arthritis staging, concomitant health conditions, pain, thumb mobility measurements, and disability ratings. Secondary data on treatment adherence via an exercise log and self-reported disability will also be captured (Michigan Hand Questionnaire) for secondary analyses.

Lastly, participants will be asked to report on adverse events during each encounter during weeks 1-6.

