15.0 Statistical Considerations

MEDICAL PROTOCOL (HRP-590)

PROTOCOL TITLE: Mechanisms of a Dynamic Stability Approach

VERSION DATE: 05/25/2023

15.1 Data Analysis Plan: For aim #1, the within-subjects outcomes will be compared primarily on the mean change in degree of subluxation from baseline to 9 week follow-up (the primary outcome). Additionally, given our recent retrospective findings²⁷ which support that advanced arthritic radiographic staging is also a negative predictor of response to the DS, mean change scores will be compared and adjusted for according to arthritic staging through use of linear regression for added precision of the treatment effect estimates. For aim #2, the agreement between baseline radial subluxation measurements via CT measurements and those via sonography will be assessed using the Bland-Altman method.⁴²

15.2 Power Analysis:

Aim #1: Previous work⁸ suggested that the mean immediate misalignment change in the treatment group will be 0.33 cm, with a standard deviation of 0.18. The proposed sample size was estimated a priori assuming a paired t-test of the change in misalignment, with two-tailed type I error of 0.05 and power of 90%. We conservatively estimate that the minimum clinically important change in misalignment will be between 0.05cm and 0.40cm, depending on how much the sustained effect is attenuated relative to the immediate effect (published value 0.42cm), and that the standard deviation (SD) of the misalignment measurement is 0.22cm. The correlation between the pre and post measurements is unknown, so we estimate the needed sample size for a range of correlation values between 0.20 and 0.80.

If we conservatively assume that the immediate misalignment change is 0.30cm, that the sustained change will be reduced by 50% to 0.15cm, and that the pre and post measurements will only be weakly correlated with a correlation coefficient of 0.2, then a sample size of 39 people (39 pre and post measurements) will be required. Assuming a potential loss-to-follow-up rate of 20%, we will enroll 49 participants.

Aim #2: A formal sample size estimate is not available for this aim given its novelty. However, because a sample of 30 participants is assumed to be adequate for bivariate correlational research³⁷, we anticipate that our sample of 49 participants will be adequately powered.

15.3 Statistical Analysis: See section 15.1.

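### Section 10.1 permits enrolment of only 40, but section 15.2 needs 49 enrolled (39 pairs) for its 90% power; at 40 with the planned 20% loss, design-case power is about 84%

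*Combined protocol and SAP*

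**What the plan says.** Section 10.1 gives the local accrual range: "we plan to enroll as many as 50 and as few as 40 participants".

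Section 15.2 sizes Aim 1 by a paired t-test on the pre-post change, two-sided at 5%, for 90% power. Its design case is a sustained change of 0.15 cm, a measurement SD of 0.22 cm and a pre-post correlation of 0.2, and it concludes "then a sample size of 39 people (39 pre and post measurements) will be required". It then adds "Assuming a potential loss-to-follow-up rate of 20%, we will enroll 49 participants". It treats the correlation as unknown: "we estimate the needed sample size for a range of correlation values between 0.20 and 0.80".

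The other enrolment figures agree with section 15.2:
- Section 1.1, Aim 1: "Fifty patients will be enrolled in a prospective pre-post interventional study".
- Section 5.2: 49 participants are to have ultrasound.
- Sections 1.1 (Aim 1a) and 11.1: 16-17 participants in each of three Eaton stages, so 48 to 51.
- Section 11.1: the race and ethnicity targets are 30, 9, 5 and 5, which sum to 49.

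**The concern.** Sections 10.1 and 15.2 both speak of enrolling, so they count the same thing, yet they set different minimums. A team that closed recruitment at 40 would comply with section 10.1 while falling 9 short of the number that section 15.2 says is needed. Forty participants also cannot fill three strata of 16-17.

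What is at stake is how the primary result is read. The protocol states 90% power without saying that this depends on the upper part of the permitted enrolment range. If recruitment ended near 40 and losses were near the planned rate, a null result would be somewhat less informative than the stated power suggests.

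**Working it through.** **Inputs, all from section 15.2 unless noted.** Change δ = 0.15 cm; SD of one measurement σ = 0.22 cm; correlation ρ = 0.2 (range 0.20 to 0.80); two-sided α = 0.05; power 90%; loss 20%. Enrolment floor 40 (section 10.1).

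**Step 1: reproduce the plan's figures.**
- SD of the change = σ√(2(1 − ρ)) = 0.22 × √1.6 = 0.2783 cm.
- Standardised change = 0.15 / 0.2783 = 0.539.
- Power is taken from the noncentral t distribution with n − 1 degrees of freedom and noncentrality 0.539√n. It is 89.9% at n = 38 and 90.7% at n = 39, so 39 pairs are needed.
- Enrolment = 39 / (1 − 0.20) = 48.75, rounded up to 49.

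Both stated figures reproduce exactly.

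**Step 2: apply the same calculation at the floor.**
- 40 × 0.80 = 32 pairs, which is 39 − 32 = 7 short.
- Keeping 39 pairs out of 40 enrolled would allow one loss: 1/40 = 2.5%.

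| Enrolled | Loss | Pairs | Power at 0.15 cm, ρ = 0.2 |
|---|---|---|---|
| 49 | 20% | 39 | 90.7% |
| 40 | 10% | 36 | 88.2% |
| 40 | 20% | 32 | 84.0% |

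The chance of missing a true 0.15 cm change therefore rises from 9.3% to 16.0%.

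**Step 3: precision at ρ = 0.2.**
- Change detectable with 90% power: 0.148 cm at 39 pairs, 0.165 cm at 32.
- 95% CI half-width = t × 0.2783 / √n: 0.090 cm at 39 pairs, 0.100 cm at 32.

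**Step 4: how far the result depends on the correlation** (δ = 0.15 cm).

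| ρ | Pairs for 90% | Enrolment at 20% loss | Power with 32 pairs |
|---|---|---|---|
| 0.2 | 39 | 49 | 84.0% |
| 0.3 | 34 | 43 | 88.4% |
| 0.34 | 32 | 40 | 90% (reached at 0.336) |
| 0.4 | 30 | 38 | 92.6% |
| 0.5 | 25 | 32 | 96.2% |

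Enrolment is pairs / 0.8, rounded up. The shortfall is gone above a correlation of about 0.34, so most of the 0.20-0.80 range is unaffected.

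**Step 5: could the stage-adjusted analysis make up the difference?** Section 15.1 says "mean change scores will be compared and adjusted for according to arthritic staging through use of linear regression for added precision". Assume equal strata, stage fitted with 2 degrees of freedom (29 error degrees of freedom at 32 pairs), and a residual SD of 0.2783√(1 − R²). Power at 32 pairs is then 83.8% at R² = 0, 87.4% at 0.10 and 89.2% at 0.15, reaching 90% at R² of about 0.17. The document gives no figure for the share of variance in change that stage explains.

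**The case against.** The strongest reply is that nothing is miscalculated. Section 15.2 commits to 49, the range in section 10.1 contains 49, and a local accrual range neither replaces the sample-size section nor calls 40 a target or a closing rule. Section 16.4 plans 50-60 record reviews to allow for drop-outs, which also suggests that about 50 was intended. This supports 49 as the working number, but it leaves 40 as the only stated enrolment minimum, with no explanation and no power attached.

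The second reply is that 84% needs several unfavourable conditions at once: enrolment at the floor, the full 20% loss, the lowest correlation in the range, and a rounded-down effect. Section 15.2 cites an immediate change of 0.33 cm and lowers it to 0.30 cm before halving. Half of 0.33 is 0.165 cm, for which 32 pairs give 90.1% power at correlation 0.2. Half of the published 0.42 cm is 0.21 cm, which gives 98.5%. These figures are right, and they limit the weight of the point. Against them, section 15.2 also contemplates changes as small as 0.05 cm, where power is low either way (16.6% at 32 pairs, 19.4% at 39). The 90% claim is tied to 0.15 cm and correlation 0.2, because those are the values the plan chose to be sized on.

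The third reply is that the loss is small: the CI half-width grows by 0.01 cm, power stays above 80% in the design case, and Aim 1 is descriptive. That also stands, and it is why the point is minor.

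It is possible that 40 was meant as completers, in which case power would be 91.4%. The text says enrol, however, under a heading that reads "Local Number of Participants to be consented".

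**Conclusion.** The inconsistency is real and minor. Section 10.1 permits a study that does not deliver the power stated in section 15.2: 32 pairs and 84.0% in the plan's own design case, against 39 pairs and 90.7%. The 84% rests on 40 enrolled, 20% loss, a 0.15 cm change, SD 0.22 cm, correlation 0.2 and an unadjusted paired t-test. It improves with lower loss, a higher correlation, a larger true change or a strongly prognostic stage effect. The study remains workable at 40; what is missing is a statement of what that size can detect. The mix of consented and enrolled in section 10.1 is a small matter of wording and adds nothing to this conclusion.

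**What to change.** Choose one of two edits.

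1. Keep the floor of 40 and add to section 15.2: *If 40 are enrolled, 20% loss leaves 32 pairs and power of about 84% for 0.15 cm at correlation 0.2 (88% at 0.3, 93% at 0.4).* This costs only the disclosure of a slightly less favourable power.
2. If 40 was not intended, change section 10.1 to: *We plan to enroll 49 participants (see 15.2).* This means recruiting up to 49 − 40 = 9 more than the present minimum. The figure of fifty in Aim 1 should be brought into line at the same time.

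With either edit, say in section 10.1 whether the number counts consented or enrolled participants. No procedure or analysis changes.
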